### **3.6 Risks and benefits**

The risk to subjects in this trial will be minimized by compliance with the inclusion/exclusion criteria, close clinical monitoring, and minimal study duration which will be planned as 1,5 years enrollment time and 6 months follow up.

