Patients who discontinue study drug should not be considered withdrawn from the study, unless one of the conditions listed above have been met. The sponsor should be notified about any decision regarding discontinuation of the study medication. Patients who discontinue the study drug should be treated according to the best standard of care. In addition to scheduled visits, patients who discontinue study drug due to adverse events or abnormalities on safety monitoring tests must be followed up with additional visits as needed in order to confirm the resolution of abnormalities. A Study Drug Discontinuation CRF should be completed, giving the date and primary reason for stopping the study drug.

For patients who are lost to follow-up (i.e. those patients whose status is unclear because they fail to appear for study visits without stating an intention to withdraw), the investigator should show "due diligence" by documenting in the source documents steps taken to contact the patient, e.g. dates of telephone calls, registered letters, etc.

Patients who are prematurely withdrawn from the study will be replaced by an equal number of newly enrolled patients.

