## **9.8 Sample size calculation**

Due to the lack of previous studies using all of the cytokines and chemokines and multitudinous analyses, it is difficult to estimate a precise sample size for our study. Despite this, our previous publications indicate that the basal IL-17 concentration is normally distributed with a mean of 32 pg/ml ( $\pm$ stdev of 15 pg/ml) in RRMS patients. If the true difference in the mean concentration of matched pairs is 7 pg/ml, we will need to study 50 pairs of subjects to be able to reject the null hypothesis with a power of 90%. The Type I error probability associated with this test of this null hypothesis is 0,05.

With assumption of drop out rate of 20% minimum 60 RRMS patients and 60 healthy control subjects should enroll to the study. Due to expected high rate of screen failure patients, we decided to screen 80 RRMS patients in order to reach 60 eligible RRMS subjects for the study.

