5.1. SAMPLE SIZE CALCULATION

Due to the lack of previous studies using all of the cytokines and chemokines and multitudinous analyses, it is difficult to estimate a precise sample size for our study. Despite this, our previous publications indicate that the basal IL-17 concentration is normally distributed with a mean of 32 pg/ml (\pm stdev of 15 pg/ml) in RRMS patients. If the true difference in the mean concentration of matched pairs is 7 pg/ml, we will need to study 50 pairs of subjects to be able to reject the null hypothesis with a power of 90%. The Type I error probability associated with this test of this null hypothesis is 0,05.

With assumption of drop out rate of 20% minimum 60 RRMS patients and 60 healthy control subjects should enroll to the study. Due to expected high rate of screen failure patients, we decided to screen 80 RRMS patients in order to reach 60 eligible RRMS subjects for the study.

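### Protocol 9.8 and SAP 5.1 inflate for 20% drop-out while Protocol 5.4.9 replaces every withdrawal; nothing links the two, and 60 enrolled from 80 screened falls slightly short under either

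*Protocol*

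**What the plan says.** Protocol 9.8 and SAP 5.1 carry the same calculation, built on IL-17 with a baseline SD of 15 pg/ml in RRMS patients. The planning condition is "If the true difference in the mean concentration of matched pairs is 7 pg/ml", for which 50 pairs are said to give 90% power. On alpha, the text is "The Type I error probability associated with this test of this null hypothesis is 0,05", with no statement of one or two sides.

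Drop-out is then added: "With assumption of drop out rate of 20% minimum 60 RRMS patients and 60 healthy control subjects should enroll to the study". Screening follows: "we decided to screen 80 RRMS patients in order to reach 60 eligible RRMS subjects for the study". The reason given for the 80 is screen failure, not drop-out.

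Protocol 5.4.9 has its own provision: "Patients who are prematurely withdrawn from the study will be replaced by an equal number of newly enrolled patients". It sets no cap, no visit limit and no end date. It does not refer to the 20% allowance. Protocol 9.8 and SAP 5.1 do not refer to replacement, and the SAP does not mention it anywhere.

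The number 80 is also used differently elsewhere. The Protocol synopsis (Population), Protocol 3.1 and 4, and SAP 4 and 5 give it as the number of RRMS patients recruited or included.

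**The concern.** An allowance for drop-out and a replacement rule address the same loss. If withdrawn patients are replaced, the completers are restored and the allowance is not needed. If the allowance is meant to absorb the loss, replacement is not needed. The plan has both and does not say whether the second is additional to the first.

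Three quantities depend on the answer: how many patients receive fingolimod, how many complete to Visit 3, and what power the within-patient comparisons have. A site reading 5.4.9 would keep enrolling. A statistician reading only the SAP would not know that replacements exist.

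**Working it through.** **Inputs.** From Protocol 9.8 and SAP 5.1: difference 7 pg/ml, SD 15 pg/ml, alpha 0.05, power 90%, 50 pairs, drop-out 20%, 60 enrolled, 80 screened. From Protocol 5.4.9: one-for-one replacement.

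Two assumptions are needed:
- The test is two-sided.
- The 15 pg/ml, given as a between-patient baseline SD, serves as the SD of the paired differences. With an SD of 15 at both visits this amounts to a within-patient correlation of 0.5, since 15 x sqrt(2 x (1 - 0.5)) = 15.

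**Step 1: reproduce the 50.** n = (SD x (z0.975 + z0.90) / difference)² = (15 x (1.960 + 1.282) / 7)² = 48.25, so 49 by the normal approximation. The noncentral t gives 51. Power at 50 pairs is 89.9% (t) or 91.0% (normal). A one-sided test would need only 40 to 41. The stated 50 is therefore reproduced, two-sided.

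**Step 2: reproduce the 60 and the 80.** 50 x 1.2 = 60. The inflation that would leave 50 after 20% loss is 50 / (1 - 0.20) = 62.5, so 63. For screening, 60 / 80 = 75% eligible, so the implied screen failure is 25%.

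**Step 3: no replacement.** 60 x 0.8 = 48 pairs. Paired power at 48 is 88.6% (noncentral t). Holding 50 pairs needs 63 enrolled and 63 / 0.75 = 84 screened.

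**Step 4: replacement from a base of 50.**
- One round: 50 + 10 = 60 enrolled and 60 / 0.75 = 80 screened, exactly the stated figures.
- That gives 50 completers only if no replacement drops out (40 + 10). If replacements also leave at 20%, it gives 40 + 8 = 48.
- Continuing until 50 complete: 50 / 0.8 = 62.5 enrolled and 62.5 / 0.75 = 83.3 screened (63 and 84 in whole patients).
- If each patient completes with probability 0.8, the chance that 60 enrolled are enough for 50 completers is about 32%.

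**Step 5: replacement on top of the 60.**
- One round: 60 + 12 = 72 enrolled and 72 / 0.75 = 96 screened.
- Continuing until 60 complete: 60 / 0.8 = 75 enrolled and 75 / 0.75 = 100 screened. Paired power at 60 is 94.5%.

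| Reading | Enrolled | Screened at 75% eligible | Expected completers | Paired power |
|---|---|---|---|---|
| 60, no replacement | 60 | 80 | 48 | 88.6% |
| Replace until 50 complete | about 63 | 83 to 84 | 50 | 89.9% |
| Replace until 60 complete | 75 | 100 | 60 | 94.5% |

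**Step 6: the other meaning of 80.** If 80 is the number enrolled, 75 fits within it. Even without replacement, 80 x 0.8 = 64 would complete.

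**The case against.** The strongest reply is that two safeguards against attrition may be redundant without being contradictory. The sample size sections call 60 a minimum, which does not bar further enrolment, and they never say that losses go unreplaced. This stands, and it limits the point to a missing link between the sections.

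A reader might infer that 60 enrolled and 80 screened fit only the inflation rule. The documents do not support that. Step 4 shows that one round of replacement from 50 gives the same two numbers, and proper inflation of 50 gives 63, not 60.

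A reader might also infer that replacement cannot be carried out because 80 screened leaves nobody spare. That treats 80 as a firm screening cap, while several sections make it the number recruited or included. It also assumes a target of 60 completers, which the plan never sets; 75 enrolled and 100 screened is the upper case. Timing does not settle the matter either. Protocol 3.6 gives "minimal study duration which will be planned as 1,5 years enrollment time and 6 months follow up". Assuming uniform accrual over 18 months and uniform drop-out over 6 months, 3 / 18, or about one sixth of withdrawals, would fall after enrolment closes. The documents give neither pattern, and most withdrawals could still be replaced.

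Finally, the primary objective is the comparison with healthy controls. The patients' baseline sample is taken at Visit 1 and all MS patients are analysed, so later withdrawal removes nothing from the control versus Visit 1 comparison. Protocol 9.8 also does not say that its pairs are visits. The SAP, however, plans paired tests only between visits and independent-sample tests against controls, so the visit comparisons are the ones to which a paired power can apply.

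**Conclusion.** The point holds in a limited form. Drop-out is provided for twice with no text linking the provisions, and at the plan's own 20% the stated figures do not quite deliver under either. The shortfall without replacement is 2 pairs (48 against 50), with paired power of about 88.6% instead of 90%. With replacement, expected needs exceed the stated 60 and 80 by 3 enrolled and 3 to 4 screened for 50 completers. If replacement is applied on top of the 60, they exceed them by up to 15 enrolled and 20 screened.

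The counts assume 75% eligibility, inferred from 60 and 80, and that replacements drop out at the same 20%. The power figures also need the two-sided test and the use of 15 pg/ml as the SD of the differences, which the documents do not justify. The completer counts do not depend on that SD. The consequence is confined to the within-patient visit comparisons and the number of patients treated.

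**What to change.** State one rule and use it in Protocol 5.4.9, Protocol 9.8 and SAP 5.1. Either choice is acceptable.

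- **No replacement.** Delete the replacement sentence in 5.4.9, say in 9.8 and SAP 5.1 that withdrawn patients are not replaced, and restate paired power as about 88.6% for 48 expected completers. If the sponsor wants to keep 50 pairs, the figures become 63 enrolled and 84 screened.
- **Replacement up to a stated number of completers.** Remove the 20% inflation and restate the expected enrolled and screened figures (about 63 and 83 to 84 for 50 completers). Add the rule to the SAP, and say when replacement stops and whether the data of replaced patients stay in the analysis set.

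In the same edit, say whether 80 is the number screened or enrolled, and align the Protocol synopsis, Protocol 3.1 and 4, and SAP 4 and 5 with Protocol 9.8 and SAP 5.1.

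The cost is a few sentences. The first option needs no extra patients but states a slightly less favourable power. The second, or holding 50 pairs in the first, adds about 3 enrolled and 3 to 4 screened to the stated figures.

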#### **5.4.10 Study completion and post-study treatment**

The investigator must provide follow-up medical care for all patients who are prematurely withdrawn from the study, or must refer them for appropriate ongoing care.

#### **5.4.11 Early study termination.**

The study can be terminated at any time for any reason by Novartis. Should this be necessary, the patient should be seen as soon as possible and treated for a prematurely withdrawn patient. The investigator may be informed of additional procedures to be followed in order to ensure that adequate consideration is given to the protection of the patient's interests. The investigator will be responsible for informing IRBs and/or ECs of the early termination of the trial.

## **6 Visit schedule and assessments**

Table 6-1 and Table 6-2 lists all of the assessments and indicates with an "x" when the visits are performed.

**Table 6-1 Assessment schedule for MS Patients**

Visit	1	2	3
Day	0	90±7	180±14
Obtain Informed Consent	X		
Evaluation of Inclusion/Exclusion Criteria	X		
Demographic and Previous Data	X		
Other Concomitant Diseases	X		
MS and Treatment History	X		
Assessment of the MS Relapses Within Last 2 Years	X		
Recording of Relapses			X
Pregnancy Test (Urine)	X		
Varicella-Zoster Ab	X		
Hematology *	X**	X	X
Clinical Chemistry *	X**	X	X
ECG	X		
Optical Cohorence Tomography	X	X	
EDSS Measurements	X		X
PASAT Measurements	X		X
Symbol Digit Modalities Test (SDMT) Measurements	X		X
9-Hole Peg Test	X		X
25 Foot Walk Test	X		X
Collecting Serum and Blood Samples for Biomarker Research	X	X	X
Dispense Study Medication	X	X	
First Dose Administration	X		
End of the Study Visit			X

\* Hematology: Leukocytes, Hemoglobin, Absolute Neutrophilis, Absolut, Lymphocyte, Platelet  
 Clinical Chemistry: AST, ALT, BUN, Creatinine, Total Cholesterol, Tryglicerides, LDL-K, HDL-K, TSH,ST4, Glucose, HbA1c

\*\* If the patient has hematology and clinical chemistry results within the last 1month, the tests do not have to be repeated.

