### **2.2 Secondary objectives**

Secondary objective of this study is:

-To test the predictive value of cytokine/chemokine changes measured in the 3rd and 6th months on the PASAT, SDMT, 9-Hole peg test, timed 25-foot walk, EDSS and relapse rate observed after 6 months of treatment.

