### **3      Investigational plan**

#### **3.1    Study design**

This study is a multi center, open label study.

80 relapsing remitting MS (RRMS) patients will be recruited according to the Mc Donald's criteria and 60 healthy controls will be recruited as the control group. All subjects will sign an informed consent that will be approved by the local Ethics Committee and the applicable health authorities prior to venipuncture. Basal EDSS, relapses during the last 2 years, paced auditory serial addition task (PASAT), 9-Hole peg test, timed 25-foot walk and single digit modalities test (SDMT) scores will be recorded before study entry. Serum and blood samples will be collected from each participant after evaluation for inclusion and exclusion criteria. Additional serum and blood samples at 2 different time points will be collected from MS patients at months 3 ( $\pm 1$  week) and 6 ( $\pm 2$  weeks) after starting fingolimod 0.5 mg/day po. treatment (Figure 1). Serum samples will be stored at -20°C at local centers for a longest duration of two weeks and kept frozen at -80°C

[figure not shown]
until assayed. The levels of IL-4, IL-6, IL-8, IL-9, IL-10, IL-13, IL-17, IL-23, IFN- $\gamma$ , TNF- $\alpha$ , VLA4, CCL2, CCL5, CXCR3, CXCL13 will be measured by ELISA according to the manufacturer's protocols. Optical density (OD) will be measured at 450 nm and cytokine/chemokine concentrations (pg/ml) will be calculated by referring to a standard curve.

Whole blood samples will be dispatched

In order to perform flow cytometry assay for intracellular cytokine measurement PBMC will be isolated freshly.

EDSS and relapses will be recorded after 6 months of treatment. PASAT, 9-hole peg test, timed 25-foot walk and SDMT's will be performed only at study entry and termination after 6 months (Figure 1).

**Figure 1:** Study protocol (PASAT: Paced auditory serial addition task, SDMT: single digit modalities test, FACS: Flow assisted cell sorting, flow cytometry)

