#### **5.4.9 Discontinuation of study treatment and premature patient withdrawal**

Patients may voluntarily withdraw from the study for any reason at any time. They may be considered withdrawn if they state an intention to withdraw, fail to return for visits, or become lost to follow-up for any other reason.

If premature withdrawal occurs for any reason, the investigator must make every effort to determine the primary reason for a patient's premature withdrawal from the study and record this information on the Study Completion CRF.

The investigator should discontinue study treatment for a given patient or withdraw the patient from study if, on balance, he/she believes that continuation would be detrimental to the patient's well-being.

Study drug must be discontinued for a given patient if the investigator determines that continuing it would result in a significant risk for that patient. The following conditions/events may be considered sufficient to support a decision about the study drug discontinuation in individual cases:

- serious adverse event (e.g. cardiac failure, diagnosed malignancy)
- abnormal laboratory value(s) including liver function tests or abnormal test result(s) (e.g. PFTs, MRI and ophthalmic findings). See below and Appendix 7 and 8 for guidance for safety monitoring
- withdrawal of consent (e.g., in case the patient does not consent to continue in the study after a confirmed relapse or disability progression)
- pregnancy
- use of prohibited medications, listed in Section 5.1 and 6.6.5
- adverse events
- protocol violation
- unsatisfactory therapeutic effect
- patient's condition no longer requires study treatment
- administrative problems (e.g. patient's non-compliance)

In addition, the following conditions based on the Guidance on safety and ophthalmic monitoring should result in study drug discontinuation:

- Hepatic Increase in ALT > 5 x ULN Increase in AST > 5 x ULN
- New neurological symptoms accompanied by MRI findings unexpected for MS
- Diagnosis of macular edema

---

- Decrease in visual acuity with abnormal OCT (increase in central foveal thickness of > 20% compared to screening or cystic changes in the macula).

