**Table 6-2 Assessment schedule for Healthy Control Group**

Visit	1	2	3
Day	0	90±7	180±14
Obtain Informed Consent	X		
Evaluation of Inclusion/Exclusion Criteria	X		
Collecting Serum and Blood Samples	X		

Patients should be seen for all visits on the designated day with an allowed “visit window” of “7” days at visit 2 and “14” days at visit 3 , or as close to it as possible, or as shortly after it as possible, or as shortly before it as possible, etc.

At a minimum, patients will be contacted for safety evaluations during the 30 days following the last study visit or following the last administration of study treatment if there are post-treatment follow-up visits (whichever is later), including a final contact at the 30-day point. Documentation of attempts to contact the patient should be recorded in the source documentation.

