#### **6.4.1 Efficacy assessment**

MS Relapses and EDSS is the key efficacy assessment criteria. Efficacy assessment will be performed at the end of the study.

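### On-study relapses are scheduled for recording only at Visit 3, so patients who leave earlier have no planned relapse assessment, and no counting window ties relapses to the marker changes

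*Protocol*

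**What the plan says.** In Protocol Table 6-1 the row "Recording of Relapses" has a mark under Visit 3 and none under Visit 2. The text agrees with the table. Protocol section 3.1 says "EDSS and relapses will be recorded after 6 months of treatment", and Protocol section 6.6 and SAP section 4 repeat it. Section 6.4.1 says "MS Relapses and EDSS is the key efficacy assessment criteria" and adds "Efficacy assessment will be performed at the end of the study". Late recording is therefore the plan, not a misprint in the table.

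The schedule has no early-withdrawal assessment. On premature withdrawal, Protocol section 5.4.9 requires the primary reason to be entered on the Study Completion CRF. Its list of grounds for stopping the drug illustrates withdrawal of consent with the case where "the patient does not consent to continue in the study after a confirmed relapse or disability progression". The same section replaces withdrawn patients with new ones. The 30-day contact described below Table 6-2 is for safety evaluation and does not mention relapses.

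The secondary objective (Protocol section 2.2, SAP section 3.2) is to predict clinical outcomes, relapse rate among them, from marker changes at months 3 and 6. For relapses on treatment, SAP section 6.2 says only that rates will be evaluated. It gives no time at risk, no rule for incomplete follow-up and no period over which relapses count.

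**The concern.** Two things are at stake.

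The first is who contributes to the relapse rate. With one scheduled recording point at the end, the rate rests on patients who reach Visit 3. The protocol itself foresees that a relapse may be why a patient does not get there. Loss of this kind can depend on the outcome, and replacing leavers restores the head count without restoring the missing relapses.

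The second is the order of events. A marker change at month 3 can predict only what happens after month 3. If onset is not tied to Visit 2, relapses that came before the month-3 sample could be counted as predicted by it. The month-6 change has the same difficulty in full, because its sample is taken at the visit where relapses are recorded.

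**Working it through.** **Inputs from the documents.** Visit 2 at day 90±7 and Visit 3 at day 180±14 (Table 6-1); drop-out of 20% and a minimum of 60 RRMS patients (Protocol 9.8, SAP 5.1). The 60 is reproduced as 50 × 1.2 = 60. The plan gives no sample size or expected rate for relapses, so there is no relapse figure to reproduce.

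**Patients without a planned relapse record.** 0.20 × 60 = 12. If the 80 patients named in Protocol 3.1 all enrol, 0.20 × 80 = 16. Replacement changes these counts but gives leavers no relapse assessment.

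**Look-back at Visit 3.** 180 − 14 = 166 to 180 + 14 = 194 days from day 0. With a relapse item at Visit 2 as well, the longest interval to cover would be 194 − 83 = 111 days.

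**Effect on the rate.** Let completers relapse at rate r and leavers at rate k × r, with equal follow-up (k and equal follow-up are assumptions):

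true rate = 0.8r + 0.2kr; observed rate = r.

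- k = 1: true rate 1.0r, no bias.
- k = 1.5: true rate 1.1r; 1/1.1 = 0.909, about 9% low.
- k = 2: true rate 1.2r; 1/1.2 = 0.833, about 17% low.

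If leavers contribute less time at risk, their weight in a rate per unit of follow-up falls, and the shortfall with it.

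**The same question from the other side.** Let p be the true 6-month relapse proportion, and let relapsing patients be R times as likely to leave, with 20% leaving overall (p and R are assumptions). The probability of leaving without a relapse is L = 0.2 / ((1 − p) + Rp). The proportion seen in completers is p(1 − RL) / 0.8. For p = 0.2 and R = 2: L = 0.2/1.2 = 0.167, and 0.2 × 0.667/0.8 = 0.167.

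| True proportion | R = 1 | R = 2 | R = 3 |
|---|---|---|---|
| 10% | 10% | 8.0% | 6.25% |
| 20% | 20% | 16.7% | 14.3% |
| 30% | 30% | 26.0% | 23.4% |

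**Timing.** The month-3 sample falls nominally at 90/180 = 50% of follow-up. If relapses are evenly spread (an assumption), about half have their onset before it. The month-6 sample is taken at Visit 3, so every relapse recorded there precedes or coincides with it. The objective's phrase about outcomes seen after 6 months cannot mean a later period, because Protocol section 4 follows patients for 6 months only.

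**The case against.** The strongest reply is that the plan leaves more trace of relapses than Table 6-1 suggests. Steroid use goes into the CRF without being tied to Visit 3 (Protocol 5.4.6). A withdrawal caused by a relapse should appear as the primary reason on the Study Completion CRF. Clinic and visit notes are kept as source documents (Protocol 8.1). A reader might infer that relapses in early leavers are never recorded; the documents do not support that. What stands is that none of these sources is designated for the relapse analysis, and a mild or untreated relapse may appear in none of them.

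A reader might also infer that Visit 3 relies on six months of undated memory. No section says so, and the CRF is not among the documents. The relapse definition in Protocol 6.4 uses the time since onset of the preceding event, and section 5.4.6 delays blood sampling until at least one month after steroids end, so sites need some dates. What stands is that the plan does not require an onset date.

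It is also tempting to say that the SAP counts early relapses as predicted by month-3 change. It specifies no predictive analysis, so the fair criticism is that the counting window is undefined.

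Finally, the primary objective compares patients with controls and is unaffected, and Protocol 9.5 plans no special hypothesis. That limits the weight of the point but does not remove it, since section 6.4.1 gives relapses a key role.

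**Conclusion.** The point holds in a limited form and should be addressed. As written, the plan gives about 12 of 60 patients, at its own 20% drop-out, no planned assessment of a key efficacy outcome, and it names a relapse as one possible reason for leaving.

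It does not follow that the relapse rate is biased low. That holds only if relapsing patients leave more often. The documents make this plausible through a single example but do not show it. The shortfall of about 9% to 17% rests on an assumed rate ratio of 1.5 to 2 and on equal follow-up; with a ratio of 1 it is zero.

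The missing counting window matters whatever the drop-out. Without it, neither the month-3 nor the month-6 marker change can be read clearly as a predictor of relapse.

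**What to change.** 1. In Table 6-1, add a mark for relapse recording at Visit 2, and add relapse recording at the last contact for anyone who leaves early. Collect the onset date each time.
2. In the SAP, include all enrolled patients in the relapse rate, both leavers and their replacements, with follow-up time as the denominator. This captures the relapse that led to leaving. Relapses after the last contact remain unseen, and the report should say so.
3. Relate month-3 marker change only to relapses with onset after Visit 2. Report the month-6 change as an association with relapse, not as a prediction.
4. Reconcile Protocol 5.4.9, under which stopping the drug does not by itself mean withdrawal, with Protocol 6.3, under which one month off drug in total does. Together they decide who reaches Visit 3.

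The cost is one more CRF item at a visit that already takes place, the same item at last contact, SAP wording, and a protocol amendment with its approvals (Protocol 11.1). The month-3 predictive analysis loses events, about half if relapses are evenly spread (an assumption). The overall relapse rate still uses them all.
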